4 ANALYSIS METHODS

The primary analysis will occur once all participants have either completed the SV10 (Week 16) assessments or have withdrawn from the study. The sponsor staff will be fully unblinded following the Primary Analysis Database Lock. Investigators, participants and site staff will not be made aware of unblinded treatment assignments for individual participants who are in the follow-up period until these participants have completed the study.

The final analysis will occur when all participants have completed the follow-up period at SV12 (Week 24) or have withdrawn from the study.

4.1 General principles

Efficacy analyses will be performed using the ITT population. Demography and baseline characteristics will be summarised by treatment group for the ITT population.

Treatment groups will be displayed as follows:

- MEDI3506 **CCI** mg
- MEDI3506 **CCI** mg
- Placebo

The standard descriptive summary statistics for a set of continuous data are n, mean, standard deviation, median, minimum value and maximum value. Other summary statistics (e.g., standard error (SE) least-squares mean (LSmean), confident interval (CI)) may be suitable in addition. For log transformed data geometric mean and coefficient of variation (CV) will be presented in addition to the standard descriptive summary statistics. Concentration data will be summarised using descriptive statistics, including n, n<lower limit of quantification, arithmetic mean, arithmetic standard deviation (SD), geometric mean, coefficient of variation (CV%), geometric mean +/- geometric SD (gSD), minimum, median, and maximum values. The geometric mean is calculated as the exponential of the arithmetic mean calculated from data on a natural log scale. The geometric CV% is calculated as $100 \times \sqrt{\exp(s^2)-1}$, where s is the SD of the data on the natural log scale. The geometric mean +/- gSD is calculated as $\exp(\text{mean}(\log(\text{PK Conc})) \pm \text{std}(\log(\text{PK Conc})))$.

For continuous data the mean, median, geometric mean, first quartile (Q1), third quartile (Q3), LSmean, CI, SD and SE will be rounded to 1 additional decimal place compared to the analysed data. Minimum and maximum will be displayed with the same accuracy as the analysed data. Coefficient of variation (CV%), where reported, will always be reported to 1 decimal place.

For categorical data, percentages will be rounded to 1 decimal place.

PK concentration descriptive statistics will all be presented as follows:

- Arithmetic mean, arithmetic SD, geometric mean, geometric CV%, Geometric Mean \pm gSD, median: 4 significant figures
- Minimum, maximum: 3 significant figures
- Data listing: same significant figures as supplied from bioanalysis.

The primary analysis will be performed after all participants have completed SV10 (Week 16) or have withdrawn from the study. At the time of the primary analysis all data collected on and prior to data cut-off date (i.e., Week 16 visit date for the last subject) will be cleaned. For the purpose of the statistical analysis, data cut-off rules might be implemented and described in a separate document.

All data collected until the time of the final DBL will be included in the final analysis. No cut-off rules will be implemented for the final analysis.

4.1.1 Statistical Hypotheses

The primary efficacy endpoint is the change from baseline in pre-BD FEV₁ at Week 16. A treatment policy estimand will be applied whereby all available data are included in the analysis, irrespective of whether a participant discontinued study intervention or received rescue therapy.

The null hypothesis is that the change from baseline in FEV₁ at Week 16 for participants dosed with MEDI3506 is equal to the change from baseline in FEV₁ at Week 16 for participants dosed with placebo. The alternative hypothesis is that the change from baseline in FEV₁ at Week 16 for participants dosed with MEDI3506 is greater than the change from baseline in FEV₁ at Week 16 for participants dosed with placebo, i.e.:

- H₀: Change from Baseline in FEV₁ at Week 16 (MEDI3506-placebo) = 0.
- H₁: Change from Baseline in FEV₁ at Week 16 (MEDI3506-placebo) > 0.

Hypothesis testing will be performed at the one-sided 10% level. If the p-value is < 0.1, reject H₀ and accept H₁. A hierarchical testing strategy will be used to preserve the type I error for the comparisons of each of the 2 dose levels of MEDI3506 versus placebo, as follows:

- Step 1: Test MEDI3506 **CC1** mg versus placebo in regard to H₀
- Step 2: If previous step rejects: test MEDI3506 **CC1** mg versus placebo in regard to H₀

4.1.2 Repeated measures mixed effects analysis of covariance model (MMRM)

The repeated measures mixed effects analysis of covariance model (MMRM) will be used to fit change from baseline for continuous endpoints at each visit, for the ITT population. The model will include all available data from all visits up to and including the target visit, irrespective of whether the participant discontinued study intervention or received rescue therapy. No imputation will be made for missing data, as a repeated measures model is being applied. The model will include fixed effects for baseline, background medication use, geographic region, baseline ICS total daily dose, visit, treatment and the baseline by visit and treatment by visit interactions. Visits within subject are considered as repeated measurements. An unstructured covariance matrix will be used to describe the correlations between observations on a participant between visits. The denominator degrees of freedom will be calculated using the Kenward-Rogers method. In the event that the model with unstructured covariance matrix fails to converge, an autoregressive (1) covariance matrix will be used instead. If also the autoregressive (1) does not converge, a compound symmetry covariance matrix will be used. If the model still does not converge, the baseline by visit effect will be deleted from the model. Estimates of the least square mean change from baseline in endpoint variable for each treatment, and the difference between them, together with two-sided 80% confidence interval, will be obtained from the model for each visit. The significance of the treatment effect will be tested at a 10% one-sided level of significance as described in Section 4.1.1.

The reportable results from the model will be:

- The least-square means (LSMeans) change from baseline at certain visit and their standard errors for each group
- The difference in change from baseline at certain visit between active treatments groups and placebo (LSMeans difference) together with its two-sided 80% confidence interval (CI)
- The one-sided p-value for the difference in change from baseline at certain visit between active treatment groups and placebo

If the dependent variable is considered to be normally distributed, the variable fitted in the model will be the change from baseline; the MMRM and the reportable results will be those described above.

On the other hand, if the dependent variable is considered to be log-normally distributed, the variable fitted in the model will be the change from baseline in logarithmical scale, with the logarithm of the baseline value as a covariate. Change from baseline in logarithmic scale is defined as the log-transformation of the post-baseline visit value minus the log-transformation of the baseline value.

The MMRM will be as described above but the reportable results from the model will be:

- For the percent change:
 - Back transformed LSmeans for each group, which correspond to the estimated percent change from baseline; back transformed LSmeans is derived as $[\text{EXP}(\text{LSMean})-1]*100$;
 - Two-sided 80% CI of the back transformed LSmeans for each group; 80% CI of the back transformed LSmeans is derived as $[\text{EXP}(\text{Lower limit of the 80\% CI of the LSmean})-1]*100$; $[\text{EXP}(\text{Upper limit of the 80\% CI of the LSmean})-1]*100$;
- For the relative change:
 - Back transformed LSmeans for each group, which correspond to the estimated relative change from baseline; back transformed LSmeans is derived as $\text{EXP}(\text{LSMean})$;
 - Two-sided 80% CI of the back transformed LSmeans for each group; 80% CI of the back transformed LSmeans is derived as $\text{EXP}(\text{Lower limit of the 80\% CI of the LSmean})$; $\text{EXP}(\text{Upper limit of the 80\% CI of the LSmean})$;
- For the comparison:
 - The estimated geometric LSMean ratio between active groups and placebo; the ratio is calculated as $\text{EXP}(\text{LSMean difference})$;
 - The Two-sided 80% CI of the ratio; the 80% CI of the ratio is calculated as $\text{EXP}(\text{Lower limit of the 80\% CI of the LSmean difference})$; $\text{EXP}(\text{Upper limit of the 80\% CI of the LSmean difference})$;
 - One-sided p-value.

Note that a ratio lower than 1 means that the active treatment group shows a higher decrease (or a lower increase) compared to the placebo group. On the other hand, a ratio greater than 1 means that the active treatment group shows a lower decrease (or a higher increase) compared to the placebo group.

The MMRM will be applied using PROC MIXED (SAS procedure).

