4 STUDY DESIGN

4.1 Overall Design

Study D9181C00001 is a Phase II, randomised, double-blind, placebo-controlled, parallel-group, proof-of-concept study to evaluate the efficacy, safety, PK and immunogenicity of MEDI3506 in adult participants with uncontrolled moderate-to-severe asthma on SOC.

Approximately 228 participants will be randomised in a 1:1:1 ratio to achieve 216 evaluable participants. Participants will receive CCI mg MEDI3506, CCI mg MEDI3506, or placebo CCI by SC injection for a total of C doses. The randomisation will be stratified according to cough sub-study participation. Note that the exploratory cough sub-study may not be activated in all countries.

Participants who fail screening can be re-screened.

Participants will be enrolled in this study for up to 29 weeks. The study comprises of 3 periods including the screening period of up to 5 weeks, an intervention period of 16 weeks, and a follow-up period of 8 weeks.

Safety data from this study will be provided to the MEDI3506 DSMB (see Appendix A 4).

Screening Period

- Participants will sign ICF and be assessed for study eligibility at SV1 (Sections 5.1 and 5.2).
- Participants assessed to have uncontrolled asthma at SV1 will undergo further baseline assessments at SV1 (see Table 1). Participants will then record adherence to their SOC asthma controller and reliever medication for a minimum period of 14 days before returning for SV2.
- At SV2, participants whose asthma remains uncontrolled despite acceptable adherence to asthma controller medication ($\geq 70\%$ adherence [days] to controller medication documented in eDiary and $ACQ-6 \geq 1.5$) will undergo further screening assessments (including echocardiogram). Participants who continue to meet all eligibility criteria will be asked to attend SV4 (randomisation) 6 to 14 days following SV2.
 - A subset of participants (up to $n = 60$, see Section 9.2 for details) who have provided optional informed consent to participate in the sub-study, will also undergo 24-hour objective cough monitoring at home, as part of an exploratory cough sub-study, commencing at SV2 and again at SV10.

Intervention Period

- Participants will be randomised at SV4 (Day 1).
- Study interventions will be administered CCI at CCI, as well as the final dose administered at CCI.
- The primary endpoint will occur at SV10 (Week 16 post initial dose of study intervention).

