- 15 In countries where spermicide is available, male participants who are sexually active with a female partner of childbearing potential must agree to use a male condom with spermicide and another highly effective method of contraception during the intervention and follow-up periods from SV4 (Day 1) through to SV12 (Week 24) of the study. In countries where spermicide is not available, male participants who are sexually active with a female partner of childbearing potential must agree to use a male condom and another highly effective method of contraception during the intervention and follow-up periods from SV4 (Day 1) through to SV12 (Week 24) of the study. See [Appendix I](#) for definitions of childbearing potential and highly effective methods of contraception. Male participants should also refrain from biologically fathering a child or donating sperm during the same period.

Informed Consent

- 16 Provision of signed and dated, written informed consent (and any locally required authorisation eg, data privacy) for study participation which includes mandatory

genotyping (study objective). Note: If a participant declines to participate in the mandatory genotyping component of the study, the participant will not be included in the study.

- 17 **Optional:** provision of signed and dated written Optional Genetic Research Information informed consent prior to collection of samples for optional genetic research that supports Genomic Initiative.

Type of Participant and Disease Characteristics

- 18 Participants with documented evidence of asthma as demonstrated by either:
- Post-BD reversibility of $FEV_1 \geq 12\%$ and ≥ 200 mL (15 to 60 min after administration of 4 puffs of albuterol/salbutamol), within 12 months prior to SV1, or at SV1 or SV2. Note: if the participant cannot perform post-BD spirometry at SV1 or needs to perform a repeat assessment of post-BD spirometry, it is also acceptable to assess this criterion at SV2, **or**
 - Positive methacholine challenge test within the 12 months prior to SV1. A positive result is defined as a $PC_{20} \leq 8$ mg/mL.
- 19 Documented history of ≥ 1 asthma exacerbation in 24 months prior to SV1 (see Section 8.1.5 for definitions of acceptable documentation and asthma exacerbation).
- 20 Morning pre-BD $FEV_1 \geq 40\%$ predicted normal and > 1 L at SV1.

Criteria to be Assessed for Exploratory Cough Sub-study

Informed Consent

- 21 Provision of written dated separate ICF for the exploratory cough sub-study.

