6.3 Measures to Minimise Bias: Randomisation and Blinding

6.3.1 Methods for Assigning Treatment Groups

All participants will be centrally assigned to randomised study intervention using an RTSM. The randomisation will be stratified according to sub-study participation. Before each site is initiated, the log in information and directions for the RTSM will be provided. The RTSM will provide to the investigator(s) or pharmacists the kit identification numbers to be allocated to the participant at the dispensing visit. Routines for this will be described in the RTSM user manual that will be provided to each centre.

Study intervention will be dispensed at the study visits summarised in SOA or per SOC after data cut off.

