9.4.2 Efficacy

9.4.2.1 Primary Endpoint

The difference in mean change from baseline in FEV₁ at Week 16 (MEDI3506 – placebo) will be estimated using a repeated measures mixed effects analysis of covariance model, for the ITT population. The model will include all available data from all visits up to and including Week 16, irrespective of whether the participant discontinued study intervention or received rescue therapy. No imputation will be made for missing data, as a repeated measures model is being applied. The model will include fixed effects for baseline, visit, treatment and the baseline by visit and treatment by visit interactions.

The significance of the treatment effect will be tested at a 10% one-sided level of significance as described in Section 9.1.

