1.2 Study design

Study D9181C00001 is a Phase II, randomised, double-blind, placebo-controlled, parallel group, proof of concept study to evaluate the efficacy, safety, PK and immunogenicity of MEDI3506 in adult participants with uncontrolled moderate to severe asthma on standard of care.

Approximately 228 participants will be randomised in a 1:1:1 ratio to achieve 216 evaluable participants. Participants will receive **CCI** mg MEDI3506, **CCI** mg MEDI3506, or placebo **CCI** by SC injection **CCI**. The randomisation will be stratified according to sub-study participation (exploratory cough sub-study).

Participants will be enrolled in this study for up to 29 weeks. The study comprises of 3 periods including the screening period of up to 5 weeks, an intervention period of 16 weeks, and a follow-up period of 8 weeks. Details of the schedule of assessment (SoA) can be found in the clinical study protocol (CSP).

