1.3 Number of participants

A sample size of 216 participants (72 participants per treatment group), randomised 1:1:1 to MEDI3506 **CC1** mg: MEDI3506 **CC1** mg: placebo, will provide at least 80% power to detect a statistically significant difference in change from baseline to Week 16 in pre-BD FEV₁, assuming a difference of 150 mL between placebo and MEDI3506, a between-participant SD of 420 mL and a one-sided- 10% alpha level. To allow for 5% participants being ineligible for the primary analysis, a total of approximately 228 participants will be randomised in the study (approximately 76/arm).

Up to 60 participants are intended to be included in the cough sub-study (approximately 20 participants per treatment group). However, given the exploratory nature of the sub-study and that it may not be activated in all countries, randomisation of participants not included in the sub-study will not be restricted, therefore, sub-study recruitment may not be achieved. Since limited data are available on cough monitoring in this population, the sub-study is considered exploratory and no formal power calculations have been performed.

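### Minor, nearly free improvement: randomisation is stratified only by cough sub-study participation, but the primary MMRM has no term for that stratum

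*SAP*

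**What the plan says.** Protocol 4.1 states: "The randomisation will be stratified according to cough sub-study participation". Protocol 6.3.1 repeats this ("The randomisation will be stratified according to sub-study participation"), as does SAP 1.2 ("The randomisation will be stratified according to sub-study participation (exploratory cough sub-study"). Neither document names a second stratification factor.

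The protocol's primary model (9.4.2.1) has no stratum term: "The model will include fixed effects for baseline, visit, treatment and the baseline by visit and treatment by visit interactions". The SAP's model (4.1.2) is longer but still has none: "The model will include fixed effects for baseline, background medication use, geographic region, baseline ICS total daily dose, visit, treatment", followed by the same two interactions. SAP section 6 records the three added covariates (background medication, geographic region, baseline ICS dose). It does not mention the stratum or say why it was left out.

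The stratum depends on a further consent (Protocol 5.1, criterion 21: "Provision of written dated separate ICF for the exploratory cough sub-study"). SAP 1.3 plans for up to 60 joiners but warns that "randomisation of participants not included in the sub-study will not be restricted, therefore, sub-study recruitment may not be achieved".

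**The concern.** When allocation is balanced on a factor that predicts outcome and the analysis ignores it, the treatment estimate gains the precision of the balance but the model does not credit it. Between-stratum variation stays in the residual, so the reported standard error is larger than the true one. The test then rejects too rarely under the null and loses some power. At stake is a small amount of efficiency on the primary endpoint, in a study planned at only just above 80% power. The factor is already recorded for every randomised participant.

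**Working it through.** **Inputs.** SAP 1.3 gives a target difference of 150 mL, an SD of 420 mL, one-sided alpha 0.10, 72 evaluable per arm in three arms, about 228 randomised and up to 60 joiners. The difference d in mean FEV1 change between joiners and non-joiners is not in the documents. It is assumed here over 0 to 300 mL.

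**The plan's own figure.** SE of the difference = 420 × √(2/72) = 70 mL, so the noncentrality is 150/70 = 2.143. Power is 80.5% by the normal approximation and 80.43% by noncentral t on 216 − 3 = 213 df. For the number randomised, 216/0.95 = 227.4, rounded up to 228. The stated figures reproduce.

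**Effect of leaving out the stratum.** The SD of 420 mL is read as the total SD, with stratum share p = 60/228 = 0.263, exact balance within strata, one visit and no other covariates.

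- Variance explained by the stratum: v = p(1 − p)d².
- Residual SD: s = √(420² − v).
- Model SE divided by true SE, when the term is omitted: r = 420/s.
- Actual size without the term: 1 − Φ(1.2816 × r).
- Power without the term: noncentral t on 213 df, noncentrality 150/(s√(2/72)), critical value multiplied by r.
- Power with the term: the same noncentrality on 212 df, with the ordinary critical value.

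Example, d = 210 mL: v = 0.2632 × 0.7368 × 44,100 = 8,551; s = √(176,400 − 8,551) = 409.7; r = 1.0252; size = 1 − Φ(1.3138) = 0.0945; power 81.02% without and 81.88% with the term.

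| d (mL) | v/420² | r | Actual size | Power without | Power with | Points forgone |
|---|---|---|---|---|---|---|
| 0 | 0 | 1.0000 | 0.1000 | 80.43% | 80.43% | 0 |
| 50 | 0.0027 | 1.0014 | 0.0997 | 80.46% | 80.51% | 0.05 |
| 100 | 0.0110 | 1.0055 | 0.0988 | 80.56% | 80.76% | 0.2 |
| 150 | 0.0247 | 1.0126 | 0.0972 | 80.73% | 81.17% | 0.4 |
| 210 | 0.0485 | 1.0252 | 0.0945 | 81.02% | 81.88% | 0.9 |
| 300 | 0.0989 | 1.0535 | 0.0885 | 81.67% | 83.43% | 1.8 |

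Power without the term rises with d because the total SD is held at 420 mL: the larger d is, the more variance the stratified allocation balances out.

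With 30 joiners instead of 60, the points forgone are 0, 0.03, 0.1, 0.3, 0.5 and 1.0.

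**Simulation check.** A single-visit linear model with 19 of 72 per arm in the stratum (40,000 trials, d = 0, 100, 210, 300 mL) gives sizes of 0.102, 0.099, 0.095 and 0.089, and power gains of 0.0, 0.2, 0.8 and 1.8 points.

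**Cost of the term if d = 0.** Moving from 213 to 212 df changes power from 80.4324% to 80.4319%, about 0.0005 points.

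**The case against.** The strongest counter-argument is that no defect has been shown. The stratum is consent to an optional exploratory sub-study that may not run in every country, and nothing in the documents says it predicts FEV1 change. The SAP already adjusts for baseline, background medication, region and ICS dose, which are more plausible predictors. Region may also absorb whatever part of a stratum difference comes from country. At differences of 50 to 100 mL, the gain is at most 0.2 points; a difference of 150 mL would equal the whole assumed drug effect.

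This stands as a limit on size: the gain may be nil, and the table shows upper-end values. It does not remove the point, because in the full-ITT linear model the term costs almost nothing whether or not the stratum matters.

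A reader might draw four stronger conclusions, none of which the documents support:

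- **Type I error is inflated.** The error runs the other way: the actual size is at or below 10%.
- **The SAP departs from the protocol.** The protocol's model has no stratum term either, so section 6 had no such change to list.
- **Power drops below 80%.** That requires the SD to be a within-stratum value and a stratum difference above about 149 mL with 60 joiners. SAP 1.3 says only "a between-participant SD of 420 mL" and brings no stratum into the calculation; the ordinary reading is the total SD.
- **The term is free in every model.** For the Cox and negative binomial models the cost has not been quantified. Hospitalised exacerbations in particular could leave the stratum with few or no events.

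**Conclusion.** The point holds as a minor, optional gain in efficiency. The only randomisation stratum is missing from the primary MMRM, and no reason is given. The primary test is valid as written, and no change in sample size follows. For assumed stratum differences up to 210 mL, the loss is at most about 0.9 power points and the actual size is no lower than about 9.4%. At 300 mL, twice the target effect, the figures are 1.8 points and 8.9%. If the stratum is unrelated to FEV1 change, the loss is zero.

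The figures rest on 420 mL as the total SD, 60 of 228 in the stratum, exact balance, one visit and no other covariates. Fewer joiners, or overlap with region, would make them smaller. They apply to the linear FEV1 comparison only.

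**What to change.** In SAP 4.1.2, add cough sub-study participation (yes/no, as randomised) as a fixed effect in the full-ITT MMRM, and list it in section 6 with the other added covariates. If the sponsor prefers to leave it out, one sentence giving the reason, written before unblinding, would be enough.

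Add a drop rule with two triggers:

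- The stratum is empty in the data being modelled, for example in a region subgroup under 4.2.4.3 where the sub-study was not activated.
- The model still does not converge after the autoregressive and compound symmetry fallbacks already listed in 4.1.2. The text should also say whether the stratum term goes before or after the baseline-by-visit term.

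The term does not apply within the cough sub-study population, where it would be constant. Extending it to the Cox and negative binomial models (4.1.5, 4.1.6) is optional and would need its own rule for sparse events.

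The cost is SAP wording and one degree of freedom. No new data are needed.

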1.3 Schedule of Activities

Once informed consent has been obtained, eDiary provision and training for site and home visits should occur first during SV1, followed by patient reported outcome (PRO) assessments. PRO assessments should be conducted first at all other visits. For all participants, in-clinic spirometry testing must be initiated between 6:00 AM and 11:00 AM during the screening or re-screening period, and randomisation visit (SV4). Whenever electrocardiograms (ECGs), vital signs, and blood draws are scheduled for the same nominal time, the order should be as follows: ECG, vital signs (vital signs can occur immediately after ECG using the same rest period), then blood draws. The timing of the first 2 assessments should be such that it allows the blood draw (eg, PK blood sample) to occur at the assigned nominal time. Whenever FeNO, airwave oscillometry (AO), and spirometry are scheduled for the same nominal time, the order should be as follows: FeNO, AO, then spirometry. Nasal sampling should be performed last, with nasal lining fluid collection performed before nasal epithelium collection (when both are scheduled). Urine samples may be collected at any time during the study visit (when scheduled). On days when investigational product is administered, all assessments should be performed pre-dose unless otherwise specified in the Schedule of Activities. Refer to Section 8 for additional information on assessment ordering (eg, pre-, post-dose or multiple timepoints within a visit). In the event that a clinical laboratory test result is not available from central laboratories during the screening period, see Section 8.2.7.

Table 1 Schedule of Activities: Screening Period

Visit Number	SV1	SV2	SV3
Procedure/Study Day	-35 to -28	-14 to -6	Visit no longer needed
Study Week	-4	-1	
Written ICF CCI /assignment of SID number	X ^a		
Written informed consent for future use and/or DNA analysis (optional)	X		
Verify eligibility criteria	X	X	
Demographics	X		
Baseline asthma assessments			
Provision of, and training on use of, home spirometry device and eDiary	X		
ACQ-6	X	X	
SGRQ		X	
SNOT-22 (comorbid CRS participants only)	X		
At-home eDiary completion and spirometry use	Twice daily throughout screening period		

Table 1 Schedule of Activities: Screening Period

Visit Number	SV1	SV2	SV3
Procedure/Study Day	-35 to -28	-14 to -6	Visit no longer needed
Study Week	-4	-1	
Assess adherence to at-home eDiary completion, spirometry, and SOC medication use		X	

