3 PRIMARY AND SECONDARY VARIABLES

3.1 General principles

3.1.1 Baseline definitions

In general, the last measurement prior to first injection of IP will serve as the baseline measurement for efficacy and safety endpoints. If Visit 4 (Day1) measurement is missing, the last non-missing value before Visit 4 (Day 1) will be used as baseline instead. If there is no result collected prior to Visit 4, then baseline value will be set to missing and will not be imputed. In the scenario where there are two assessments on Visit 4 (Day 1) prior to first dose, one with time recorded and the other without time recorded, the one with time recorded would be selected as baseline.

An exception from the general rule will be ECGs. The mean value of each parameter from the triplicate measurements at Visit 4 (Week 0) pre-dose will be used as the baseline value.

For bi-weekly summaries, such as 2-weekly mean number of night-time awakenings, 2-weekly mean daily rescue medication usage, 2-weekly mean FEV1, 2-weekly mean PEF,

baseline would be defined as the mean from last 2 weeks (14 days) results before Visit 4 (Week 0), ie from evening of Study Day -14 to the morning of Study Day 1. If there are fewer than 10 completed days in the 14-day baseline period (where a complete day = entry from the evening AND the following morning) then baseline will be set to missing.

For CompEx analysis the mean from last 2 weeks (14 days) results before Visit 4 (Week 0) should be derived separately for morning and evening assessments. If there are fewer than 7 completed days in the 14-day baseline period (where a complete day = entry from the evening AND the following morning) then baseline for CompEx event will be set to missing. To note: PEF is expected to be collected with 3 measurements for each morning and evening assessment. The maximum value provided by the vendor (both morning and evening for the 2-weekly mean analysis and separately for the CompEx analysis) should be used to derive the baseline and any post-baseline assessments.

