3.3 Derivation of primary variable

The primary efficacy variable is the pre-bronchodilator (BD) forced expiratory volume in the first second (FEV₁) (L). Pre-BD FEV₁ (L) will be measured by in-clinic spirometry at visits SV1, SV2, SV4, SV6, SV7, SV8, SV9, SV10, SV11, SV12 and E/D. The primary efficacy endpoint is the change from baseline to Week 16 in pre-BD FEV₁ (L).

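### The primary FEV1 model could also adjust for the SV1 and SV2 values already collected: a nearly free gain in precision of uncertain size, not an error in the plan

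*SAP*

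**What the plan says.** SAP 3.3 says that pre-bronchodilator FEV1 "will be measured by in-clinic spirometry at visits SV1, SV2, SV4" and then at each post-dose clinic visit. SAP 3.1.1 sets the baseline rule: "In general, the last measurement prior to first injection of IP will serve as the baseline measurement for efficacy and safety endpoints". An earlier value becomes baseline only when the Visit 4 value is missing.

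The generic model in SAP 4.1.2, which 4.2.4.1 applies to the primary endpoint, reads: "The model will include fixed effects for baseline, background medication use, geographic region, baseline ICS total daily dose, visit, treatment". It also has baseline-by-visit and treatment-by-visit terms. There is therefore one FEV1 covariate and no SV1 or SV2 term.

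Protocol 1.3 and 8.1.1.1 put spirometry at screening and at SV4 in the same 6–11 AM window, on centrally supplied equipment. Protocol 6.5.3 gives one withhold list for all scheduled site spirometry. The SV1 value is tested against eligibility limits (inclusion criteria 6 and 20). The SV2 value enters eligibility only through reversibility, if that is tested at SV2.

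SAP 1.3 sizes the trial "assuming a difference of 150 mL between placebo and MEDI3506, a between-participant SD of 420 mL and a one-sided- 10% alpha level", with 72 per group, and says this "will provide at least 80% power to detect a statistically significant difference".

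**The concern.** A single spirometry session carries visit-to-visit noise. Two further sessions in the five weeks before dosing hold information about each participant's usual level that SV4 alone does not. Where that is so, leaving them out gives the Week 16 difference a larger standard error than the collected data allow.

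The SAP already averages repeat measurements elsewhere: triplicate ECGs, 14-day diary baselines and repeat FeNO readings. It also adds three covariates to the protocol's model (SAP section 6). It gives no reason for stopping at one FEV1 value.

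Power matters here because testing is hierarchical (SAP 4.1.1): if the first dose comparison fails, the second dose is not tested.

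**Working it through.** **1. The plan's own figure.** Inputs from SAP 1.3 and 4.1.1: difference 150 mL, SD 420 mL, 72 per arm, one-sided alpha 0.10 (z = 1.2816).

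- SE = 420 × √(2/72) = 70.0 mL.
- Power = Φ(150/70.0 − 1.2816) = Φ(0.861) = 80.5%.
- The same formula needs 71 per arm for 80% power.

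The stated power is met without SV1 or SV2.

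**2. Assumptions, none of them in the documents.** The between-person FEV1 SD is 0.6 to 0.8 L. The within-person variance is scaled so that the SV4 to Week 16 change has SD 420 mL. SV1 and SV2 sit at the middle of their windows: Day −31.5 (−4.5 weeks) and Day −10 (−1.4 weeks). The within-person part is pure visit noise, half noise and half slow drift (8-week time constant), or all drift.

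**3. One case in full** (between-person SD 0.6 L, pure noise).

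- Within-person variance = 0.42²/2 = 0.0882. Total = 0.36 + 0.0882 = 0.4482. Correlation ρ = 0.36/0.4482 = 0.803.
- Residual variance given SV4 = 0.4482 × (1 − ρ²) = 0.159, so SD 399 mL.
- Residual variance given SV4 and the SV1/SV2 mean = 0.4482 × [1 − 3ρ²/(1 + 2ρ)] = 0.115, so SD 340 mL.
- SD ratio = 340/399 = 0.85.

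**4. All cases.** SAP 1.3 does not say whether 420 mL is the SD of raw change or the SD after adjustment for SV4, so power is given both ways.

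| Within-person variation | Residual SD ratio | Power if 420 mL is SV4-adjusted (now 80.5%) | Power if 420 mL is raw change (now 82–84%) | Equivalent n per arm, 72/ratio² |
|---|---|---|---|---|
| Pure visit noise | 0.84–0.85 | 89–90% | 91% | 99–103 |
| Half drift | 0.90–0.91 | 86% | 88% | 87–89 |
| All drift | 0.96–0.97 | 82–83% | 84–85% | 77–78 |

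The gain is about 8–9, 5–6 or 2 points, on either reading of 420 mL.

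**5. Other correlation structures, with 420 mL as the SV4-adjusted SD.**

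- Equal correlation of 0.5, 0.7, 0.8 and 0.9 gives variance ratios 0.833, 0.760, 0.726 and 0.695, and power 85.7%, 88.0%, 89.1% and 90.1%.
- A stable level plus a decaying component plus noise gives variance ratios 0.78–0.95 and power 82–87%.
- Pure AR(1), with no lasting person-level difference and no session noise, gives ratio 1.00 and power 80.5%: no gain. Replacing SV4 by a plain three-visit mean would then lower power to about 79%.

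**The case against.** **The plan is complete and valid without this.** That stands. A reader might infer that the trial is underpowered or that the analysis is biased; neither follows. Stated power is met, and a last-pre-dose baseline is a legitimate choice. If 420 mL is the raw-change SD, the SV4 covariate already lifts power to 82–84%.

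**SV1 and SV2 are not equivalent to SV4.** This also stands.

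- SV1 is truncated by eligibility: at least 40% and below 85% predicted, and above 1 L.
- SV1 precedes eDiary-recorded controller adherence, which starts after it (Protocol 4.1).
- Protocol 8.1.1.1 asks that post-randomisation spirometry be, if possible, within 1.5 hours of the SV4 clock time. SV1 and SV2 may fall anywhere in a five-hour window.

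As an illustration, give SV1 and SV2 extra variance of 50–100% of the within-person variance. The SD reductions then shrink to roughly 10–14%, 6–8% and 1–2% in the three cases. This weakens the prediction but does not bias the treatment comparison, because both values precede randomisation.

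**The size is assumed.** That stands too. The calculation also leaves out the three other covariates already in the model. The zero-gain case, however, needs FEV1 in litres to have no lasting differences between people. That is hard to credit when entry spans 40% to below 85% of a predicted value specific to each participant.

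**A one-line change would leave gaps.** SAP 4.1.2 serves every MMRM endpoint, and some have only one screening value (SGRQ and oscillometry at SV2, SNOT-22 at SV1). Missing values, rescreening and the convergence fallback also need rules.

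**Conclusion.** This is a worthwhile improvement, not a correction. The direction is well supported: a covariate measured before randomisation leaves the contrast unbiased and costs a few degrees of freedom. The size is not known from the documents. Under the stated assumptions it is a 3–16% smaller residual SD and about 2–9 points of power, with zero under pure AR(1). It may be smaller because SV1 is truncated and neither screening value is clock-matched to Week 16.

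Two further inferences should be avoided. The earlier values are not wholly ignored, since one can become the fallback baseline. The FEV1 figures also do not carry over to ACQ-6 or FeNO: no calculation was made for either, and ACQ-6 must be at least 1.5 at all three pre-treatment visits.

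**What to change.** Before the primary data lock, add to SAP 4.2.4.1, not to the generic model in 4.1.2:

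- SV4 stays as the baseline for the change score and as its own covariate. Do not replace it with a three-visit mean.
- The mean of the SV1 and SV2 pre-bronchodilator FEV1, and its interaction with visit, are added as a second covariate.
- If one of the two is missing, or already serves as the fallback baseline, the other is used alone.
- For rescreened participants, the screening set that led to randomisation is used.
- If the convergence fallback removes baseline-by-visit, this interaction is removed with it.

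List the change in SAP section 6. State whether the supportive analysis in 4.2.4.2 inherits it, since that section points to 4.1.2. Extension to ACQ-6 and FeNO is optional and would need its own justification.

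The cost is a short SAP paragraph, some programming and a few degrees of freedom. No new data or visits are needed.
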